Section 10.9 – Exploratory Efficacy Endpoints	Deleted entire section	Data collection and analysis eliminated from the protocol
Original Section 10.9.6 – Quality of Life	Deleted entire section	Data collection and analysis eliminated from the protocol
Section 10.10 – Interim Analysis	An interim analysis of lesion rates and recurrences will be conducted after all viral shedding samples from Month 5 to 6 swab collection period have been tested and will include analysis of shedding and lesion rates on data collect to Month 6. The specific contents of the interim analyses will be detailed in the SAP.	Genital swabbing has been eliminated from the protocol
Appendix 1 – Schedule of Events, Serum and PBMCs	Serum for immunogenicity research purposes PBMCs for immunogenicity research purposes Eliminated at Months 6 and 12	Immunogenicity testing has been eliminated from the protocol
Appendix 1 – Schedule of Events, Daily electronic reporting tool	Subject will report the presence or absence of genital lesions, and severity of genital herpes symptoms on each day from Day 1 through Month 12 6.	Reflect new data collection period
Appendix 1 – Schedule of Events, EQ-5D-5L	Subject will complete the EQ-5D-5L on each day of the first recurrence after the maintenance dose through Month 6.	Reflect new data collection period
Appendix 1 – Schedule of Events, Administration of	Eliminated	RGHQoL has been eliminated from the protocol

Section	Change	Rationale
RGHQoL		
Appendix 1 – Schedule of Events, Instruction in anogenital swab collection; Distribution, reconciliations and processing of swabs; Swab collection	Eliminated	Genital swabbing has been eliminated from the protocol

## 1 LIST OF ABBREVIATIONS AND DEFINITIONS OF TERMS

---

Abbreviation or Term	Definition
AE	adverse event
AESI	adverse event of special interest
DMC	Data Monitoring Committee
EQ-5D-5L	EuroQol – 5 Domains – 5 Levels
IA	interim analysis
IM	intramuscular
MAAE	medically attended adverse event
MedDRA	Medical Dictionary for Regulatory Activities
mITT	Modified intent-to-treat
MM2	Matrix-M2 adjuvant
PP	Per protocol
PT	Preferred term
SAE	serious adverse event
SAP	Statistical Analysis Plan
SD	standard deviation
SOC	System Organ Class

## 2 STUDY OVERVIEW

This study is a randomized, double-blind, placebo-controlled clinical trial of GEN-003 in subjects who have received previous doses of GEN-003. Subjects who completed Study GEN-003-003 and received all 3 doses, reported data in daily electronic reporting period on at least 80% of days, and had no important protocol deviation in that trial were offered enrollment in this study. Subjects who met all inclusion and no exclusion criteria and provided written informed consent for this study were randomized within 11 to 18 months after the last active GEN-003 dose in a 1:1 ratio to receive 1 intramuscular (IM) dose (the maintenance dose) of GEN-003 or placebo. Randomization was stratified on the basis of the GEN-003 dose received by the subject in Study GEN-003-003.

Subjects were to use a daily electronic tool for reporting the presence or absence of genital herpes lesions and severity of genital herpes symptoms from Day 1 until the Month 6 visit.

Subjects were to complete the EuroQol – 5 Domains – 5 Levels (EQ-5D-5L) questionnaire on each day of the first recurrence after the maintenance dose through Month 6.

Local reactions and systemic events were to be recorded for the first 7 days after the maintenance dose on a paper Diary Card; if any event was ongoing after Day 8, it was to be followed until resolution. All adverse events (AEs) and concomitant medications were to be recorded from Day 1 to Day 29/Month 1. After Day 29/Month 1 to the end of the study, only serious AEs (SAEs), AEs of special interest (AESIs), medically attended AEs (MAAEs), antiviral medications, and vaccines were to be recorded. All AEs were to be graded in accordance with the Toxicity Grading Scale for Healthy Adult and Adolescent Volunteers Enrolled in Preventive Vaccine Clinical Trials from Grade 1 (mild) to Grade 4 (life-threatening).

From Month 2 to Month 6, the investigational site was to contact each subject monthly by telephone or site visit for review of daily electronic reporting tool data and assessment of SAEs, AESIs, and antiviral medication use (through Month 6).

A Data Monitoring Committee (DMC) was to review safety data at intervals of a minimum of 3 months until all subjects have completed the GEN-003/placebo dosing period. Any additional meetings and the specific safety monitoring plan were to be detailed in the DMC charter.

### **3 STUDY OBJECTIVES**

#### **3.1 Primary Efficacy Objective**

The primary efficacy objective is as follows:

- To evaluate the efficacy of GEN-003 versus placebo administered as a maintenance dose in reduction of genital herpes lesion rate

#### **3.2 Secondary Efficacy Objectives**

The secondary efficacy objectives are as follows:

- To evaluate the efficacy of GEN-003 versus placebo administered as a maintenance dose on genital herpes recurrence through Month 6:
- Reduction of genital herpes recurrence frequency
- Increase of proportion of subjects who are genital herpes recurrence-free
- Increase of time to first genital herpes recurrence
- Reduction of genital herpes recurrence duration

#### **3.3 Safety Objective**

- To evaluate the safety and tolerability of a maintenance dose of GEN-003 versus placebo

### **4 ANALYSIS POPULATIONS**

#### **4.1 Modified Intent-to-Treat Population**

The Modified Intent-to-Treat (mITT) population includes all randomized subjects who received the maintenance dose. Subjects will be analyzed according to the treatment to which they were randomized.

#### **4.2 Safety Population**

The Safety population includes all randomized subjects who received the maintenance dose. Subjects will be analyzed according to the treatment received.

#### **4.3 Per Protocol Population**

The Per Protocol (PP) population includes subjects who received the maintenance dose, reported data during the daily electronic reporting period on at least 80% of days, and had no important protocol deviations. Subjects will be analyzed according to the treatment received.

## **5 STATISTICAL METHODOLOGY**

### **5.1 Summarization of Data**

Study results will be summarized in tabular format by treatment group (GEN-003, Placebo), with descriptive statistics and/or in subject listings. In general, descriptive statistics for continuous variables will consist of subject count, mean, standard deviation (SD), median, and range; and descriptive statistics for categorical variables will consist of subject counts and percentages. Time-to-event data will be analyzed by the Kaplan-Meier life test method, and results will be summarized by 25th, 50th (median), and 75th percentiles with associated 2-sided 95% confidence intervals (CIs), as well as the percentage of censored observations.

The efficacy analyses described in this Statistical Analysis Plan (SAP) will be performed for the mITT and PP populations. The safety analyses will be performed for the safety population.

### **5.2 Sample Size Justification**

Sample size in this study is dependent on the enrollment in GEN-003-003. No formal sample size calculations were performed for this study.

### **5.3 Randomization**

Eligible subjects were randomized in a 1:1 ratio to receive 1 IM dose of GEN-003 (60 µg each antigen and 50 µg MM2) or placebo. Randomization was stratified on the basis of the GEN-003 dose received by the subject in Study GEN-003-003.

### **5.4 Unblinding**

#### **5.4.1 At Subject Level**

Unblinding of treatment assignment is discouraged. If a medical emergency occurs for which the identity of the treatment assignment is critical to the care of a subject, the Investigator will call the Medical Monitor to discuss. If unblinding is deemed necessary, a designated unblinded study team member (unblinded statistician) will provide the treatment assignment to the Medical Monitor who will provide the information to the Investigator.

#### **5.4.2 Interim Analysis**

The Sponsor and members of the study team will be unblinded to the treatment arms at the interim analysis time point. Only the DMC members and unblinded statistician will have access to unblinded safety data at the subject level and only at specified intervals throughout the study or as necessary to perform the task of overall safety monitoring.

#### **5.4.3 Final Analysis**

After database lock at the end of the study, individual subject treatment assignments will be unblinded and available to all study team personnel, including the lead, blinded statistician.

## **5.5 Data Handling**

### **5.5.1 Method for Handling Missing Data**

No imputation of missing data will be performed. All available safety and efficacy data will be included in data listings and summaries.

### **5.5.2 Definition of Baseline Values**

Unless otherwise specified, Baseline values are defined as the values collected on Day 1 of GEN-003-005.

### **5.5.3 Windowing of Visits**

All data will be categorized based on the scheduled visit at which it was collected. These visit designators are predefined values that appear as part of the visit tab in the electronic case report form.

### **5.5.4 Justification of Pooling**

All data from all sites will be pooled. Study center or treatment-by-center interaction will generally not be included in statistical analyses.

### **5.5.5 Withdrawals, Dropouts, Loss to Follow-up**

Time-to-event variables will be censored if a subject withdraws, drops out, or is lost to follow-up before the documentation of the time to the first subject-reported recurrence after the maintenance dose.

If a subject withdraws, drops out, or is lost to follow-up before the first recurrence after the maintenance dose is recorded, the subject will be censored at the last documented time without recurrence recorded; if no record is available after the maintenance dose, the subject will be censored at Day 1.

## **5.6 Output Production and Validation**

All analyses will be performed using SAS V 9.2 or higher (SAS Institute, Inc, Cary, North Carolina, USA). Validation and quality control of the tables, listings, and figures that display the results of the statistical analysis of the data from this study will follow the appropriate Innovative Analytics standard operating procedures.

## **6 SUBJECT DISPOSITION**

A breakdown of the number and percentage of subjects enrolled by site and treatment group will be provided. The number of subjects who complete the study will be summarized in tabular format for the safety population. Reasons for discontinuation from the study will also be summarized. A summary of analysis populations table by treatment group will be presented, and a subject listing of protocol deviations will be produced.

## **7 DEMOGRAPHIC CHARACTERISTICS**

Demographic and baseline characteristics will be summarized by treatment group.

For quantitative variables, summary statistics (number [n], mean, SD, minimum, median, and maximum) will be presented for all subjects. For qualitative variables, results will be summarized as counts and percentages for all subjects.

## **8 MEDICAL HISTORY**

All medical history events will be coded using the Medical Dictionary for Regulatory Activities (MedDRA) coding system. Medical history events (past and current medical disorders) will be presented by treatment group for the safety population, summarized by MedDRA system organ class (SOC) and preferred term (PT).

## **9 CONCOMITANT MEDICATIONS**

All medications will be coded using the World Health Organization (WHO) Drug Dictionary. Frequency tables will be presented by treatment group that summarize the prior and concomitant medications taken during the course of the study. A subject listing of medications will also be provided.

## **10 ELECTRONIC DIARY COMPLIANCE**

Summary statistics will be presented by treatment group for the electronic diary compliance after the maintenance dose.

## **11 EFFICACY ANALYSIS**

### **11.1 Genital Herpes Lesion Rate**

Lesion rate (days) is defined as number of days with lesions divided by the time period of follow-up for lesions (in days). The days with lesions will be collected continuously throughout the study via an electronic lesion diary, and lesion rates will be calculated for the following periods: Baseline and Day 1 to 183 (post-dosing). For the purposes of determining days with lesions, a diary entry of missing will be treated the same as a diary entry of “no,” except in the following case: if 1 or 2 consecutive instances of missing is flanked by “yes” values on both sides, those missing values will be treated as a “yes” value.

Lesion rate will be analyzed with descriptive summary tables for overall and individual lesion rates calculated for the periods noted above. Individual subject lesion rates will be compared for the active treatment group vs. placebo using the Wilcoxon rank sum test.

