**Table 14.2.1: Summary Statistics for Electronic Diary Compliance After Maintenance Dose by Treatment Group**

mITT Population

	GEN-003 60 ug/ M2 50 ug N=xx	Placebo N=xx
Days with Entry		
n	xx	xx
Mean	xx.xx	xx.xx
SD	xx.xxx	xx.xxx
Median	xx.xx	xx.xx
Min, Max	xx.x, xx.x	xx.x, xx.x
Days without Entry		
n	xx	xx
Mean	xx.xx	xx.xx
SD	xx.xxx	xx.xxx
Median	xx.xx	xx.xx
Min, Max	xx.x, xx.x	xx.x, xx.x
Percent Compliance		
n	xx	xx
Mean	xx.xx	xx.xx
SD	xx.xxx	xx.xxx
Median	xx.xx	xx.xx
Min, Max	xx.x, xx.x	xx.x, xx.x

Note: Days with Entry are days from Day 1 to Month 6 visit or date of discontinuation with an entry of 'Yes' or 'No'  
Days without Entry are days from Day 1 to Month 6 visit or date of discontinuation with an entry of blank

Program:

Date Produced: mm/dd/yy

Programming Notes:

- Use Day 1 as start date
- Use earliest of Month 6 visit and date of completion or early termination (dsdtdat) from Subject Disposition form as cutoff date
- Percent Compliance = Days with Entry / (Days with Entry + Days without Entry) \* 100%

[Sponsor]

Protocol: [Protocol number]

page x of y

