**Table 14.2.3.1: Descriptive Summary of Individual Subject Lesion Rates by Treatment Group and Observation Period**

mITT Population		
Visit Statistic	GEN-003 60 ug/ M2 50 ug N=xx	Placebo N=xx
Baseline		
n	xx	xx
Mean	xx.xx	xx.xx
SD	xx.xxx	xx.xxx
Median	xx.xx	xx.xx
Min, Max	xx.x, xx.x	xx.x, xx.x
Total subjects w/ at least 1 day of lesions	n (%)	n (%)
Days 1-183		
n	xx	xx
Mean	xx.xx	xx.xx
SD	xx.xxx	xx.xxx
Median	xx.xx	xx.xx
Min, Max	xx.x, xx.x	xx.x, xx.x
Total subjects w/ at least 1 day of lesions	n (%)	n (%)
Change from Baseline (Days 1-183)		
n	xx	xx
Mean	xx.xx	xx.xx
SD	xx.xxx	xx.xxx
Median	xx.xx	xx.xx
Min, Max	xx.x, xx.x	xx.x, xx.x
P-Value (vs. Placebo) [1]	0.xxxx	

Note: Lesion rate (days) is defined as number of days with lesions divided by the number of days in the observation period.

[1]P-value based on Wilcoxon rank sum test.

Program:

Date Produced: mm/dd/yy

Programming Notes:

- Present results for Baseline and Days 1-183.
- A day with lesions is a day for which LESIONS='Yes'.
- Number this table 14.2.3.1 and produce a similar table (14.2.3.2) for the PP population

[Sponsor]

Protocol: [Protocol number]

page x of y

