**Table 14.2.5.1: Proportion of Subjects Who Are Recurrence Free at 6 Months After Maintenance Dose**

mITT Population			
Variable Statistic	GEN-003 60 ug/ M2 50 ug N=xx	Placebo N=xx	P-value[1]
Recurrence Free at 6 Months after Maintenance Dose*			0.xxxx
Yes	n (%)	n (%)	
No	n (%)	n (%)	
Unknown	n (%)	n (%)	

\* 'Yes' includes subjects who do not have a recurrence from Maintenance Dose through 6 months after Maintenance Dose.

'No' includes subjects who do have a recurrence from Maintenance Dose through 6 months after Maintenance Dose.

'Unknown' includes subjects who discontinue prior to 6 months after Maintenance Dose and have not had a recurrence prior to discontinuation.

[1] From a chi-square test of homogeneity of proportions (excluding Unknown counts).

Program:

Date Produced: mm/dd/yy

Programming Notes:

- Number this table 14.2.5.1 and produce a similar table (14.2.5.2) for the PP population

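### Unentered diary days, apart from short gaps inside an outbreak, are scored as lesion-free, so a retained subject who stops the diary before any recorded lesion counts as 0% and recurrence-free in mITT

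*SAP*

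**What the plan says.** The daily electronic report is the source for the primary and all four secondary efficacy endpoints (Protocol 2.2). The plan handles an unentered day in several places:

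- **Counting lesion days (SAP 11.1).** "a diary entry of missing will be treated the same as a diary entry of" *no*. The one exception is that "if 1 or 2 consecutive instances of missing is flanked by" *yes* values on both sides; those days become *yes*.
- **Denominator.** The text of SAP 11.1 uses the follow-up time for lesions, without saying whether that means entered days, days to the Month 6 visit or 183 days. The note to Table 14.2.3.1 uses "number of days with lesions divided by the number of days in the observation period", with Days 1-183 as the period. Neither takes unentered days out.
- **General rule (SAP 5.5.1).** "No imputation of missing data will be performed".
- **Population (SAP 4.1).** mITT "includes all randomized subjects who received the maintenance dose". No minimum number of diary entries applies. The PP population requires entries on at least 80% of days (SAP 4.3).
- **Recurrence-free status (Table 14.2.5.1).** *Yes* means no recurrence through 6 months. *Unknown*, which is left out of the chi-square test, "includes subjects who discontinue prior to 6 months after Maintenance Dose and have not had a recurrence prior to discontinuation".
- **Time to first recurrence.** SAP 5.5.5 gives a censoring rule for subjects who withdraw, drop out or are lost. The note to Table 14.2.6.1 censors at the day last known to be recurrence-free, without that restriction.

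**The concern.** A subject can stay in the study, attend visits and stop using the diary. SAP 11.1 then treats silence as absence of disease, and Table 14.2.5.1 has no category for that subject other than *Yes*. The rule works mostly in one direction. An unentered day at the edge of an outbreak, within a gap of 3 or more days, or after the diary stops can only remove lesion days; only the bridged 1-2 day gap adds them.

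If one arm reports less than the other, its lesion rate falls and its recurrence-free proportion rises with no change in disease. With at most 90 subjects and no sample-size calculation, a handful of stoppers can move the result. The interim analysis takes place after the Month 6 visits, when the diary period is over. Every efficacy table flagged for it is mITT only, and SAP 5.4.2 unblinds the sponsor to treatment arms at that point.

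**Working it through.** The plan states no sample size, power or alpha, so there is no figure of its own to reproduce. The check applies the SAP 11.1 rule literally and then asks how much it matters.

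**1. The rule on test diaries.** No entries over 183 days gives 0/183 = 0%. A 1-day or 2-day gap between *yes* days is filled. A 3-day gap is not, and neither are the days after a subject stops in mid-outbreak.

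**2. One worked subject.** Take three 5-day outbreaks starting on Days 20, 80 and 140. The true rate is 15/183 = 8.20%.

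| Last entry | SAP rule, 183-day denominator | Entered days as denominator |
|---|---|---|
| none | 0/183 = 0% | not evaluable |
| Day 15 | 0/183 = 0% | 0/15 = 0% |
| Day 40 | 5/183 = 2.73% | 5/40 = 12.50% |
| Day 100 | 10/183 = 5.46% | 10/100 = 10.00% |

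The value of 0% needs the diary to stop before the first recorded lesion. At a constant 2.7 recurrences per 6 months (placebo mean in Study GEN-003-003, Protocol Table 1; Poisson assumed), the chance of no recurrence by day *s* is exp(-2.7 × *s*/182.5): 81% at Day 14, 66% at Day 28, 44% at Day 56 and 29% at Day 84.

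**3. Recurrence-free table.** Assume 45 per arm (90 at 1:1) and 6/45 = 13.3% truly recurrence-free in each arm, close to the 13% for placebo in Protocol Table 1. Add GEN-003 stoppers who would in truth have recurred.

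| Stoppers | Scored *Yes* | p | p if *Unknown* |
|---|---|---|---|
| 4 | 10/45 = 22.2% | 0.270 | 0.862 |
| 6 | 12/45 = 26.7% | 0.114 | 0.789 |
| 8 | 14/45 = 31.1% | 0.043 | 0.713 |

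**4. Simulation with no treatment effect.** Assumptions: 45 per arm, 183 days, negative binomial recurrences (mean 2.7, probability of none 13%), mean duration 4.8 days, stoppers stay in the study and stop at a uniformly random day, two-sided 0.05. With 1,500 replicates, the standard error near 5% is √(0.05 × 0.95/1500) = 0.6 points. Rejection rates:

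| Stopping | Wilcoxon, SAP rule | Wilcoxon, entered days | Chi-square, *Yes* | Chi-square, *Unknown* |
|---|---|---|---|---|
| none | 4.5% | 4.5% | 5.6% | 5.6% |
| 10% in both arms | 4.7% | 5.0% | 5.7% | 5.4% |
| 10% in GEN-003 only | 6.1% | 5.3% | 7.5% | 4.2% |
| 20% in GEN-003 only | 10.5% | 5.7% | 11.9% | 4.7% |
| 30% in GEN-003 only | 16.8% | 6.4% | 17.9% | 5.6% |

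In the extreme case where the one-arm stoppers never make an entry, 10% and 20% stopping give 12.3% and 29.1% (Wilcoxon) and 20.5% and 52.6% (chi-square) under the SAP rules.

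**5. When missing days depend on lesions.** In a second simulation (40 per arm, 169 days, 7-day missing runs, gamma shape 1.5 assumed, 400 runs, no effect), only lesion-free days went missing, at nominal rates of 30% and 5%. The SAP rule gave 6.63% in both arms and rejected 4.5% of the time. Entered days gave 9.13% against 6.95% and rejected 14%. The entered-days rate is thus unbiased only if missingness is unrelated to lesions.

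**6. What PP removes.** With a Month 6 visit on Day 169, 80% of 169 is 135.2, so fewer than 136 entries excludes a subject. Up to 169 − 136 = 33 unentered days remain possible, and outside bridged gaps each is scored *no*.

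**The case against.** The strongest case for the plan is that its rule is prespecified and identical in both arms, and may be correct: subjects who skip quiet days but log outbreaks are scored properly by it and wrongly by an entered-days rate (step 5). Conduct safeguards are substantial. Subjects had to report on at least 80% of days in the parent study, they receive daily reminders, and sites get weekly alerts and review the data weekly (Protocol 4.1 and 6.1). Noncompliance is a ground for discontinuation (Protocol 8.2), which would lead to *Unknown*. Table 14.2.1 shows compliance by arm, and every efficacy analysis is repeated in PP. Finally, this is a phase 2 study whose sponsor has stopped development.

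Much of this stands. It rules out replacing the primary denominator outright, and it makes a subject with no entries at all unlikely. It does not settle how a stopper is scored. The safeguards reduce missing days but leave the rule unchanged, PP is a subset selected after randomisation, and neither the PP tables nor Table 14.2.1 is flagged for the interim.

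A reader might infer from the reactogenicity in Study GEN-003-003 (Grade 3 in 51.2% against 13.6% on placebo) that compliance will differ by arm and so favour the vaccine. The documents do not support that. The figures are for 7 days after any of three doses, this trial gives one, and nothing links early reactions to six months of diary use or gives a direction.

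**Conclusion.** The point holds, and should be fixed. Under the SAP as written, a retained subject who stops the diary before any recorded lesion has a 0% lesion rate and is recurrence-free in mITT, and a later stopper has a diluted rate. The first result does not depend on which denominator is meant, provided at least one *no* was entered; the dilution does. SAP 5.5.1 and 11.1 contradict each other on the primary endpoint.

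The effect on the comparison is conditional. It needs missingness that differs by arm, and the sizes in step 4 rest on assumed one-arm stopping of 10% to 30%.

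Two stronger readings are tempting. One is that every unentered day counts as lesion-free and every stopper gets the best possible result. The 1-2 day bridge and the worked subject contradict that: stopping on Day 40 or Day 100 gives a non-zero rate and *No* for recurrence-free. The other is that SAP 11.1 itself creates the recurrence-free error. Its rule is worded only for counting lesion days; the classification comes from the Table 14.2.5.1 footnotes.

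**What to change.** Make these changes before unblinding, that is, before the interim analysis:

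1. In Table 14.2.5.1, extend *Unknown* to subjects with no recorded recurrence whose diary stops before the end of the period. State in SAP 5.5.5 that they are censored at the last diary entry, consistent with the note to Table 14.2.6.1.
2. Treat subjects with no post-dose entries as not evaluable for lesion rate.
3. Add a prespecified mITT lesion-rate analysis, also at the interim, that divides *yes* days plus bridged days by entered days plus bridged days. Report it beside the missing-as-*no* result and require the conclusion to hold under both, because each is right under a different assumption about why days are missing.
4. Reconcile SAP 5.5.1 with 11.1, so that the missing-as-*no* rule and the bridge are stated as exceptions.

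No new data are needed; entered days are already derived for Table 14.2.1 ("Days with Entry are days from Day 1 to Month 6 visit or date of discontinuation with an entry of" Yes or No). The cost is wording and programming, a few more *Unknown* or non-evaluable subjects, and noisier rates for poor reporters.

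Two limits remain. Changing early stoppers to *Unknown* drops those without a recorded recurrence but keeps those with one. In the step 4 simulation this lowered the affected arm's recurrence-free proportion by 0.9, 1.6 and 2.6 points at 10%, 20% and 30% stopping, where the current rule raised it by 2.5, 5.5 and 7.9. The censored Kaplan-Meier estimate should therefore be read alongside. Also, with scattered single missed days the entered-days rate runs slightly high, because the bridge adds only *yes* days: 7.3% against 6.8% at 20% and 5% missing in a null simulation with 40 per arm, with rejection at 5.7%.

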5.2 Randomization

Eligible subjects will be randomized in a 1:1 ratio to receive 1 IM dose of GEN-003 (60 μg each antigen and 50 μg MM2) or placebo.

Randomization will be stratified on the basis of the GEN-003 dose received by the subject in Study GEN-003-003.

Randomization will be achieved using the randomization component of the electronic case report form (eCRF). After subject eligibility is confirmed on this form, the system will send an e-mail to the unblinded pharmacist (or otherwise qualified personnel) with instructions for accessing the treatment assignment.

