10.7 Primary Efficacy Endpoint – Genital Herpes Lesion Rate

Genital herpes lesion rates (the proportion of days with genital lesions present) in the 6-month period after the maintenance dose will be compared between treatment groups using the Wilcoxon rank sum test.

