## **11.2 Frequency of Genital Herpes Recurrences**

The frequency of genital herpes recurrences in the 6-month period after the maintenance dose will be calculated as the number of recurrences reported using the daily electronic lesion diary, and will be summarized by mean, SD, median, and range. The median frequencies of recurrences will be compared between treatment groups using the Wilcoxon rank sum test.

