## **11.3 Proportion of Subjects Recurrence-Free**

The proportion of subjects in each treatment group who are genital herpes recurrence-free at 6 months after the maintenance dose will be tabulated and compared using a chi-square test for homogeneity of proportions.

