## **11.4 Time to First Genital Herpes Recurrence**

Time to the first subject-reported recurrence in the 6 month period after the maintenance dose will be estimated via Kaplan-Meier approach. The log rank test will be used to compare time to first recurrence between the GEN-003 and placebo arms.

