## **11.5 Duration of Genital Herpes Recurrences**

Mean lesion outbreak duration is defined as the average number of days with lesions per outbreak for those who have lesion outbreaks (recurrences).

Mean lesion outbreak duration will be presented in a similar descriptive summary table as done for lesion rate as described above. Individual subject mean outbreak duration will be summarized by treatment arm over 6 months (Days 1 to 183) after the maintenance dose. A Wilcoxon rank sum test will be used to test the hypothesis that the median mean lesion outbreak durations are the same between treatment groups at 6 months after the maintenance dose.

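### Randomization is stratified by prior GEN-003 dose, but no efficacy test uses the stratum, the optional prior-dose sensitivity analysis is undefined in the SAP, and Table 14.1.2 does not show prior dose by arm

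*SAP*

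**What the plan says.** Both documents describe the same stratified 1:1 allocation. Protocol 5.2: "Randomization will be stratified on the basis of the GEN-003 dose received by the subject in Study GEN-003-003". SAP 5.3: "Randomization was stratified on the basis of the GEN-003 dose received by the subject in Study GEN-003-003". Entry requires all three active doses in the parent study (Protocol 4.1), which had two active arms (Protocol 1.5.5), so there are two strata: 60 µg of each antigen with 50 µg or with 75 µg of MM2.

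The efficacy tests are plain two-group comparisons:

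- Lesion rate, SAP 11.1: "Individual subject lesion rates will be compared for the active treatment group vs. placebo using the Wilcoxon rank sum test". Protocol 10.7 likewise says that rates "will be compared between treatment groups using the Wilcoxon rank sum test".
- Recurrence frequency, SAP 11.2: "The median frequencies of recurrences will be compared between treatment groups using the Wilcoxon rank sum test".
- Recurrence-free proportion, SAP 11.3: "compared using a chi-square test for homogeneity of proportions".
- Time to first recurrence, SAP 11.4: "The log rank test will be used to compare time to first recurrence between the GEN-003 and placebo arms".
- Recurrence duration, SAP 11.5: "A Wilcoxon rank sum test will be used to test the hypothesis" of equal medians.

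Protocol 10.8 matches the four secondary tests. Protocol 10.2 leaves open sensitivity analyses that use the parent-study assignment, but names neither endpoints nor method. The SAP text and its table list contain nothing corresponding. The Table 14.1.2 shell has rows for age, sex, race, ethnicity and weight only. Listing 16.2.2.2 may show prior dose subject by subject, but its shell is not given and it would not be a summary by arm.

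**The concern.** Stratified allocation removes between-stratum variation from the treatment contrast. An unstratified test leaves that variation in its null variance, so it becomes conservative and loses some power when the strata differ. In the parent study's Table 1 the two active arms did differ on some measures: 22% against 36% recurrence-free six months after the last dose, and 3.3 against 4.3 days mean duration. Protocol 3.2.1 nevertheless describes their clinical efficacy as similar.

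The second issue is pre-specification. Diary collection ends at Month 6. The interim that follows includes the mITT tables for lesion rate and every secondary efficacy endpoint (SAP 14 and table list), and SAP 5.4.2 unblinds the sponsor and study team to the arms at that point. A prior-dose analysis that is only permitted could then have its endpoints and method chosen with results in hand. Protocol 10 requires SAP deviations to be described in the study report, which would disclose such a choice but not make it pre-specified.

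**Working it through.** **No stated figure to reproduce.** Protocol 10.1 and SAP 5.2 give no sample size or power calculation, so the check sizes the effect of ignoring the stratum.

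**Inputs**

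- Size ceiling: parent arms of 43 and 44, less 2 per arm who stopped dosing for safety (Protocol 1.5.5): (43 − 2) + (44 − 2) = 83. Sizes of 70, 60, 50 and 40 are assumptions.
- Strata (recurrences, recurrence-free after last dose, duration in days), from Table 1: 50 µg arm 2.1, 22%, 3.3; 75 µg arm 1.9, 36%, 4.3; placebo 2.7, 13%, 4.8.
- *Equal*: both strata at the mean of the active arms (2.0, 29%, 3.8). *Table 1*: each stratum at its own values. *Larger gap* (assumption): one stratum at the 50 µg values, the other at placebo values.
- Effect: the 41% reduction in Protocol 1.5.5 (ratio 0.59), all on recurrence rate or split between rate (× 2.1/2.7) and duration.
- Model (assumption): negative binomial recurrence counts with dispersion matched to the recurrence-free share; duration 1 + Poisson with a gamma subject effect, shape 3. 40,000 replicates per cell; simulation error about 0.1 point under the null and at most 0.25 for power.

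**Test statistics.** In stratum s with n subjects (n1 active, n0 placebo), let W be the active rank sum, E = n1(n + 1)/2 and V = n1·n0/[n(n − 1)] · Σ(r − r̄)². Van Elteren: Z = Σ[(W − E)/(n + 1)] / √Σ[V/(n + 1)²]. The planned Wilcoxon test ranks all subjects together: Z = (W − E)/√V.

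**Lesion rate, power in %**

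| Subjects | Strata | Wilcoxon / van Elteren, effect on rate | Wilcoxon / van Elteren, split effect |
|---|---|---|---|
| 83 | Equal | 38.6 / 38.4 | 29.4 / 29.1 |
| 83 | Table 1 | 37.9 / 38.9 | 29.0 / 30.0 |
| 83 | Larger gap | 54.0 / 55.1 | 44.8 / 46.5 |
| 50 | Equal | 24.8 / 24.6 | 19.5 / 19.1 |
| 50 | Table 1 | 24.9 / 25.4 | 19.7 / 20.2 |
| 50 | Larger gap | 33.7 / 35.6 | 27.7 / 29.7 |

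Over all sizes the largest gain was 2.7 points (60 subjects, larger gap, split effect: 33.0 to 35.7) and the largest loss 0.5 (70 subjects, equal strata: 33.7 to 33.2). In the larger-gap case type I error was 4.0–4.2% for Wilcoxon and 4.8–5.1% for van Elteren. A repeat simulation at 83 subjects gave 38.0 / 37.7, 37.4 / 38.3 and 53.5 / 54.5. At 50 subjects with the larger gap, the difference ran from −0.7 to +4.3 points depending on how the arms split within strata, averaging about 2.

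**A simpler model.** Gamma-Poisson lesion days (shape 0.7, 183 days), 22 per arm per stratum, ratio 0.59, 5,000 runs (error about 0.3 point under the null, 0.7 for power):

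| Stratum mean lesion rates | Type I error, Wilcoxon / van Elteren | Power, Wilcoxon / van Elteren |
|---|---|---|
| 4.5%, 4.5% | 4.7 / 4.9 | 36.6 / 36.2 |
| 4.5%, 6.0% | 5.0 / 5.1 | 36.1 / 36.1 |
| 4.5%, 7.9% | 4.6 / 4.9 | 34.7 / 36.0 |
| 4.5%, 13.5% (extreme) | 3.9 / 5.1 | 31.0 / 37.0 |

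**Chi-square, analytically.** Ratio of within-stratum to pooled variance at 22% and 36%: [(0.22 × 0.78 + 0.36 × 0.64)/2] / (0.29 × 0.71) = 0.2010/0.2059 = 0.976. Large-sample type I error is 2[1 − Φ(1.96/√0.976)] = 4.7%.

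**Secondary endpoints, power in %, unstratified / stratified**

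| Endpoint | Strata | 83 subjects | 50 subjects |
|---|---|---|---|
| Frequency (rate effect) | Table 1 | 43.5 / 44.8 | 28.7 / 29.2 |
| Log-rank (rate effect) | Table 1 | 29.5 / 31.1 | 20.1 / 20.8 |
| Duration (split effect) | Equal | 44.7 / 43.9 | 28.4 / 27.7 |
| Duration (split effect) | Table 1 | 42.7 / 43.8 | 27.0 / 27.9 |
| Duration (split effect) | Larger gap | 47.2 / 50.7 | 28.3 / 32.2 |
| Chi-square / CMH (rate effect) | Equal | 24.6 / 24.9 | 17.5 / 16.2 |
| Chi-square / CMH (rate effect) | Table 1 | 23.7 / 24.9 | 17.3 / 16.5 |
| Chi-square / CMH (rate effect) | Larger gap | 32.2 / 32.3 | 22.2 / 20.1 |

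Duration excludes recurrence-free subjects, as the Table 14.2.7.1 note requires. CMH is Cochran-Mantel-Haenszel.

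**The case against.** The strongest reply is that nothing is broken. The two documents name the same test for each endpoint, ignoring the stratum did not inflate type I error, and the gain on the documents' own figures is about a point or less for lesion rate. A larger gain needs one group of fully vaccinated subjects to behave like parent-study placebo, while Protocol 3.2.1 calls the two doses similar. All of that stands, and it sets the priority.

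Four caveats on the figures also stand:

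- Table 1 covers the six months after primary dosing, whereas subjects here enter 11 to 18 months after their last dose. The documents give no prior-dose difference for that period.
- The inputs imply lower lesion rates than those stated: 2.1 × 3.3/183 = 3.8% against 4.5%, and 2.7 × 4.8/183 = 7.1% against 7.9%.
- The figures are for the post-dose lesion rate, as SAP 11.1 is worded, but the Table 14.2.3.1 shell prints its p-value under change from baseline.
- The chi-square ran at up to 6.1% under the null near 50 subjects, so part of its advantage over CMH there is excess type I error.

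It is also fair that a sensitivity analysis cannot displace the named primary test, and that stratified allocation promotes balance whether or not the test uses the stratum. Neither point defines the open analysis or puts the achieved balance in a table.

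**Conclusion.** The concern holds, as an optional improvement. All its textual parts are confirmed. Stratifying the lesion-rate test is worth about 0 to 1 point of power with Table 1 strata and about 1 to 3 points under the assumed larger gap. It costs at most about 0.5 point if the strata are equal. The unstratified rank tests remain valid and become mildly conservative only when the strata differ strongly. These sizes rest on the simulation model, on sample sizes below 83 being assumed, on Table 1 values carrying over to a later period, and on a 41% effect from the primary series applying to a maintenance dose. The pre-specification gap does not depend on those assumptions, but its stakes are limited because Protocol Appendix 6 (Amendment 2) records that development has stopped.

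**What to change.** Before the Month 6 unblinding, specify in the SAP:

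- Lesion rate: van Elteren test stratified by prior GEN-003 dose, with the unstratified Wilcoxon test kept as a sensitivity analysis.
- Recurrence frequency and duration: van Elteren test.
- Time to first recurrence: stratified log-rank test.
- Recurrence-free proportion: CMH alongside the planned chi-square, not in its place, because CMH lost about 1 to 2 points near 50 subjects.
- Table 14.1.2: a row for prior GEN-003 dose by arm.

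This takes SAP text, standard procedure options and one table row, with no new data. The power cost is at most about 0.5 point for lesion rate and 0.8 point for duration, both with equal strata. Because Protocol 10.7, 10.8 and the synopsis name the unstratified tests, changing the lead tests also needs a protocol amendment submitted for IRB/EC approval (Protocol 11.6). If that is not worthwhile, keep the planned tests as lead and pre-specify the stratified ones as the sensitivity analysis that Protocol 10.2 already permits, plus the baseline row; that is a SAP change only. If unblinding has already happened, label the stratified results post hoc.
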